#### 4.6.2 Definition of Dose-Limiting Toxicities

A DLT is defined as any of the following events that occur during the 21-day DLT evaluation period, except those that are clearly due to underlying disease or extraneous causes.

A hematologic DLT is defined as:

Event	Severity
Febrile neutropenia or neutropenic infection	Grade 3 or 4
Neutropenia lasting > 7 days	Grade 4
Thrombocytopenia	Grade 4
Thrombocytopenia with clinically significant bleeding	Grade 3
Thrombocytopenia requiring a platelet transfusion	Grade 3
Anemia	Grade 4
Anemia requiring transfusion	Grade 3

A non-hematologic DLT is defined as:

Event	Severity
Hy's law case	AST and/or ALT > 3x ULN and bilirubin > 2x ULN, and without initial findings of cholestasis (serum alkaline phosphatase (ALP) activity < 2x ULN) and no other reason that could explain the combination of increased transaminases and serum total bilirubin, such as viral hepatitis A, B, or C, preexisting or acute liver disease, or another drug capable of causing the observed injury.
Hypersensitivity/infusion-related	Grade 3 or higher. A Grade 3 hypersensitivity /

reaction (regardless of premedication)	infusion-related reaction that resolves within 24 hours after onset with appropriate clinical management does not qualify as a DLT.
All other non-hematologic toxicity	Grade 3 & 4

The following conditions are not considered non-hematologic DLTs:

Event	Severity
Fatigue	Grade 3 for $\leq$ 7 days.
Diarrhea, nausea, or vomiting	Grade 3 in the absence of premedication that responds to therapy and improves by at least 1 grade within 3 days for Grade 3 events or to $\leq$ Grade 1 within 7 days.
Serum lipase or serum amylase	Grade 3 for $\leq$ 7 days if without clinical signs or symptoms of pancreatitis.
Electrolyte abnormalities	$\leq$ Grade 3 which normalize within 48 hrs (with or without medical intervention) and which do not manifest themselves clinically; in such instance, a follow-up sample MUST be taken within 48 hrs to check whether such normalization has occurred.

Patients who experience a DLT that resolves or stabilizes with appropriate medical management may continue treatment at the discretion of the Investigator in consultation with the Sponsor.

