## 5.2 Guidelines for Dose Modification: Hematologic Toxicities

Adverse Event	Grade	ADCT-502 Management Guideline
Febrile neutropenia	3	Hold ADCT-502 until the patient recovers. Up to 1 dose of ADCT-502 may be skipped to permit improvement. Consider use of granulocyte colony stimulating factor (G-CSF) as per institutional guidelines or as per ASCO guidelines. G-CSF prior to ADCT-502 is not allowed unless approved by sponsor.

Adverse Event	Grade	ADCT-502 Management Guideline
		
First Occurrence:
 
If patient recovers from febrile neutropenia prior to next scheduled dose or within 21 days from last scheduled (but missed) ADCT-502 dose, then continue ADCT-502 at 1 dose level below the original assigned dose in subsequent treatment cycles. If the patient does not recover within 21 days from the last scheduled (but missed) ADCT-502 dose, permanently discontinue ADCT-502.
 
Second Occurrence:
 
Permanently discontinue ADCT-502 if febrile neutropenia recurs despite ADCT-502 dose reduction.

Febrile neutropenia	4	Permanently discontinue ADCT-502.
Thrombocytopenia with significant bleeding or platelet transfusion required as per PI assessment	3	
Hold ADCT-502 until bleeding has stopped and improvement has occurred to <math>\leq</math> Grade 1. Up to 1 dose of ADCT-502 may be skipped to permit improvement.
 
First Occurrence:
 
Upon improvement to <math>\leq</math> Grade 1 within 21 days from last scheduled (but missed) ADCT-502 dose, continue ADCT-502 at 1 dose level below the original assigned dose in subsequent treatment cycles.
 
If improvement to CTCAE <math>\leq</math> Grade 1 does not occur within 21 days from the last scheduled (but missed) ADCT-502 dose, permanently discontinue ADCT-502.
 
Second Occurrence:
 
Upon improvement to <math>\leq</math> Grade 1 within 21 days from last scheduled (but missed) ADCT-502 dose, continue ADCT-502 at 2 dose levels below the original assigned dose in subsequent treatment cycles.
 
If improvement to <math>\leq</math> Grade 1 does not occur within 21 days from the last scheduled (but missed) ADCT-502 dose, permanently discontinue ADCT-502.
 
Third Occurrence:
 
Permanently discontinue ADCT-502.

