Neutropenia or thrombocytopenia (in the absence of bleeding)	3	
Hold ADCT-502 until improvement to <math>\leq</math> Grade 1. Up to 1 dose of ADCT-502 may be skipped to permit improvement. Consider use of G-CSF as per institutional guidelines or as per ASCO guidelines. G-CSF prior to ADCT-502 is not allowed unless approved by sponsor.
 
First Occurrence:
 
If improvement to <math>\leq</math> Grade 1 within 21 days from last scheduled (but missed) ADCT-502 dose, then continue ADCT-502 at original assigned dose in subsequent treatment cycles.
 
If improvement to <math>\leq</math> Grade 1 does not occur within 21 days from the last scheduled (but missed) ADCT-502 dose, permanently discontinue ADCT-502.
 
Second Occurrence:
 
If improvement to <math>\leq</math> Grade 1 within 21 days from last scheduled (but missed) ADCT-502 dose, then continue ADCT-502 at 1 dose level below the original assigned dose in subsequent treatment cycles.
 
If improvement to <math>\leq</math> Grade 1 does not occur within 21 days from the last scheduled (but missed) ADCT-502 dose, permanently discontinue ADCT-502.
 
Third Occurrence:
 
Permanently discontinue ADCT-502

Neutropenia	4	
Hold ADCT-502 until improvement to <math>\leq</math> Grade 1. Up to 1 dose of ADCT-502 may be skipped to permit improvement. Consider use of G-CSF as per institutional guidelines or as per ASCO guidelines. G-CSF prior to ADCT-502 is not allowed unless approved by sponsor.
 
First Occurrence:
 
If improvement to <math>\leq</math> Grade 1 within 21 days from last scheduled (but missed) ADCT-502 dose, then continue ADCT-502 at original assigned dose in subsequent treatment cycles. If improvement to <math>\leq</math> Grade 1 does not occur within 21 days from the last scheduled (but missed)

Adverse Event	Grade	ADCT-502 Management Guideline

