	3	Hold ADCT-502 until improvement to $\leq$ Grade 1 or Baseline. Up to 1 dose of ADCT-502 may be skipped to permit improvement.  First Occurrence:  If improvement to $\leq$ Grade 1 or Baseline occurs prior to next scheduled dose, continue ADCT-502 at the original assigned dose at the next scheduled treatment cycle.  If improvement to $\leq$ Grade 1 or Baseline within 21 days from last scheduled (but missed) ADCT-502 dose, continue ADCT-502 at 1 dose level below the original assigned dose in subsequent treatment cycles. If improvement to $\leq$ Grade 1 or Baseline does not occur within 21 days from the last scheduled (but missed) ADCT-502 dose, permanently discontinue ADCT-502.  Second Occurrence:  If improvement to $\leq$ Grade 1 or Baseline within 21 days from last scheduled (but missed) ADCT-502 dose, then continue ADCT-502 at 2 dose level below the original assigned dose in subsequent treatment cycles. If improvement to $\leq$ Grade 1 or Baseline does not occur within 21 days from the last scheduled (but missed) ADCT-502 dose, permanently discontinue ADCT-502.  Third Occurrence:  Permanently discontinue ADCT-502.
Hyperbilirubinemia	2	Hold ADCT-502 until improvement to $\leq$ Grade 1 or Baseline. If improvement to $\leq$ Grade 1 or Baseline occurs prior to next scheduled dose, continue ADCT-502 at the original assigned dose at the next scheduled treatment cycle.  First Occurrence:  If improvement to $\leq$ Grade 1 or Baseline within 21 days from last scheduled (but missed) ADCT-502 dose, continue ADCT-502 at 1 dose

Adverse Event	Grade	ADCT-502 Management Guideline
		
level below the original assigned dose in subsequent treatment cycles. If improvement to <math>\leq</math> Grade 1 or Baseline does not occur within 21 days from the last scheduled (but missed) ADCT-502 dose, permanently discontinue ADCT-502.
 
Consider close monitoring as needed.
 
Second occurrence:
 
Permanently discontinue ADCT-502
 
Permanently discontinue ADCT-502 for any case meeting Hy's Law criteria.

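### Two dose-modification rules give conflicting instructions: Grade 3 thrombocytopenia transfused without bleeding (Section 5.2), and a second Grade 2 hyperbilirubinemia that clears before the next dose (Section 5.3)

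*Protocol*

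**What the plan says.** **Thrombocytopenia, Grade 3 (Protocol Section 5.2).** Two rows matter.

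- Row A is headed "Thrombocytopenia with significant bleeding or platelet transfusion required as per PI assessment". On recovery to Grade 1 or better within 21 days of the missed dose, the first-occurrence instruction is to "continue ADCT-502 at 1 dose level below the original assigned dose in subsequent treatment cycles". The second-occurrence instruction is to "continue ADCT-502 at 2 dose levels below the original assigned dose in subsequent treatment cycles".
- Row B is headed "Neutropenia or thrombocytopenia (in the absence of bleeding". On the same recovery condition, the first-occurrence instruction is "then continue ADCT-502 at original assigned dose in subsequent treatment cycles" and the second-occurrence instruction is "then continue ADCT-502 at 1 dose level below the original assigned dose in subsequent treatment cycles".

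The DLT table in Section 4.6.2 lists "Thrombocytopenia requiring a platelet transfusion" as a Grade 3 event on its own line, apart from thrombocytopenia with clinically significant bleeding.

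**Hyperbilirubinemia, Grade 2 (Protocol Section 5.3).** Ahead of the *First Occurrence* heading, the row says that if improvement to Grade 1 or baseline "occurs prior to next scheduled dose, continue ADCT-502 at the original assigned dose at the next scheduled treatment cycle". Further down, the second-occurrence line calls for permanent discontinuation and attaches no condition on recovery time.

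**Discretion.** Section 5 places resumption after any suspension with the investigator in consultation with the sponsor. Section 4.6.2 says much the same for patients who continue after a DLT.

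**The concern.** A dose-modification table should send each patient to one instruction. Here two kinds of patient are sent to two.

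The Grade 3 thrombocytopenia rows are divided by bleeding, but Row A also has a trigger that is not bleeding: a platelet transfusion. Row B's only qualifier for thrombocytopenia is that there is no bleeding, and it does not exclude transfused patients. The rows therefore overlap. The case is not contrived, because the protocol's own DLT table treats transfusion and bleeding as separate Grade 3 events.

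In the Grade 2 bilirubin row, the early-recovery sentence stands outside any occurrence heading and so reads as applying to every occurrence. It then meets an unconditional stop at the second.

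At stake is the dose given after a serious hematologic event in the first case, and whether treatment goes on at all in the second. Any such case would also feed SAP outputs. SAP Section 4.7.1 tabulates cumulative dose by dose level, and SAP Section 4.8.2.1 counts TEAEs leading to delay, reduction or interruption.

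**Working it through.** The plan states no figure to reproduce. The check sets the rows side by side and then sizes the gap from Table 9 (Appendix 18.4.1).

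**1. Grade 3 thrombocytopenia, transfused, no bleeding**

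| Situation | Row A | Row B | Agree? |
|---|---|---|---|
| First occurrence, recovery within 21 days of missed dose | 1 level below | original dose | No |
| Second occurrence, same recovery | 2 levels below | 1 level below | No |
| No recovery within 21 days | discontinue | discontinue | Yes |
| Third occurrence | discontinue | discontinue | Yes |

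The rows differ by one dose level wherever they differ.

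**2. Size of one level**

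Table 9 levels (µg/kg): 30, 60, 120, 150, 180, 210, 240, 300, 350, 400, 450, 500. First-occurrence gap = (assigned dose − next lower level) / assigned dose.

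- 60: 30/60 = 50%. 120: 60/120 = 50%.
- 150: 30/150 = 20%. 180: 30/180 = 16.7%. 210: 30/210 = 14.3%. 240: 30/240 = 12.5%.
- 300: 60/300 = 20%. 350: 50/350 = 14.3%. 400: 50/400 = 12.5%. 450: 50/450 = 11.1%. 500: 50/500 = 10%.

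Example at 240 µg/kg: 210 (Row A) against 240 (Row B) at the first occurrence, then 180 against 210 at the second.

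Two limits on these figures:

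- Section 2.4 lists provisional levels without 150 and 210. On that list the gap would be 60/240 = 25% at 240 and 60/180 = 33.3% at 180. The percentages depend on the list used; the one-level difference does not.
- Where there are too few lower levels to step down to (for example, two below 60 µg/kg), a reduction instruction has no target. That gap also affects bleeding patients who meet only Row A. It is a separate matter and is not counted here.

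**3. Grade 2 hyperbilirubinemia**

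| Situation | Text ahead of the occurrence headings | Text under the occurrence heading | Agree? |
|---|---|---|---|
| First, recovers before next dose | original dose | silent | Yes |
| First, recovers within 21 days of missed dose | not triggered | 1 level below | Yes |
| First, does not recover in that time | not triggered | discontinue | Yes |
| Second, recovers before next dose | original dose | discontinue | **No** |
| Second, recovers later or not at all | not triggered | discontinue | Yes |

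Exactly one situation conflicts. In the Grade 3 rows for anemia, transaminases and bilirubin, the equivalent early-recovery sentence sits under the first-occurrence heading. The Grade 2 bilirubin row is the exception. The Hy's Law line in that row is a separate override and plays no part in the conflict.

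**4. Does any other text settle it?**

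- Section 5.1 covers events not specified in Sections 5.2 to 5.4. These events are specified, so it does not apply.
- Sections 4.6.2 and 5 say who decides on continuing or resuming. They name neither a row nor a dose level.
- The Grade 4 thrombocytopenia row states that it applies with or without significant bleeding, so it avoids the problem. The Grade 3 pair has no such wording.

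**The case against.** The strongest reply has four parts.

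- **These are guidelines, and the sponsor is consulted.** Both thrombocytopenia rows require a hold, so every case in the overlap comes to the investigator and sponsor before re-dosing. This stands as a limit on the consequence. A reader might infer that sites would diverge unnoticed, each in full compliance; the documents do not support that. But consultation does not say which instruction governs.
- **The more specific text should win.** Row A names transfusion and Row B looks like the residual row; the second-occurrence bilirubin line is more specific than the sentence above it. These readings are reasonable, but the protocol states no such rule, and both Grade 3 headings carry their own qualifier.
- **DLT data and the MTD are untouched.** This stands. The transfusion event is a DLT only if it falls in the 21-day evaluation period in Part 1, and a second occurrence will ordinarily come later. The mCRM uses the DLT outcome of that period, while the disputed dose is given afterwards. A reader might infer that the conflict distorts MTD selection; it does not.
- **The trial ended early.** SAP Section 3.3 reports that Part 2 was not performed, so a correction has little practical effect left in this trial. This also stands, though the text did govern Part 1.

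**Conclusion.** Both conflicts are in the protocol as written, and both are narrow.

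- Grade 3 thrombocytopenia with transfusion and no bleeding: the two applicable rows differ by one dose level at the first and second occurrence, given recovery within 21 days of the missed dose. They agree on non-recovery and on a third occurrence.
- Grade 2 hyperbilirubinemia: the conflict is between the original dose and permanent discontinuation, and only for a second occurrence that recovers before the next scheduled dose. A reader might infer that the whole row contradicts itself; it does not.

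This is an internal inconsistency in instructions that bear on patient safety. It is softened by sponsor consultation and has no effect on MTD selection. The conclusion rests on reading the headings literally and on the absence of any ranking rule. The documents do not show whether any patient fell into either case, and the effect on exposure or safety summaries cannot be sized from them.

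**What to change.** - **Section 5.2:** reword the two Grade 3 thrombocytopenia headings so that a transfused, non-bleeding patient belongs to one row only.
- **Section 5.3, Grade 2 hyperbilirubinemia:** reconcile the early-recovery sentence with the second-occurrence line, so that it is clear which occurrences the sentence covers and the two cannot both apply.

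The sponsor decides which instruction applies in each case; no dose or clinical rule is proposed here.

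The cost is two row headings and one sentence by amendment, with no added data or patients. Since Part 2 did not take place, the main remaining use is in any later protocol that reuses these tables. If either case arose in Part 1, the study report can state which instruction was followed.

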## 5.1 ADCT-502 General Dose Modification Guidelines

Guidelines for management of specific toxicities are detailed in [Sections 5.2, 5.3, and 5.4](#). For management of events not specified in these sections, the following may serve as a guidance to investigators:

AE Grade	ADCT-502 Management Guideline
1	No dose adjustment is required.
2	
First Occurrence:
 
Consider holding ADCT-502 until improvement to <math>\leq</math> Grade 1 or Baseline. Up to 1 dose of ADCT-502 may be skipped to permit improvement. If improvement to <math>\leq</math> Grade 1 or Baseline occurs within 21 days from the last scheduled (but missed) ADCT-502 dose, continue ADCT-502 at the original assigned dose level in subsequent treatment cycles.
 
If improvement to <math>\leq</math> Grade 1 or Baseline does not occur within 21 days from the last scheduled (but missed) ADCT-502 dose, permanently discontinue ADCT-502.
 
Second Occurrence:
 
Hold ADCT-502 until improvement to <math>\leq</math> Grade 1 or Baseline. Up to 1 dose of ADCT-502 may be skipped to permit resolution. If improvement to <math>\leq</math> Grade 1 or Baseline occurs within 21 days from the last scheduled (but missed) ADCT-502 dose, continue ADCT-502 at 1 dose level below the original assigned dose in subsequent treatment cycles. If improvement to <math>\leq</math> Grade 1 or Baseline does not occur within 21 days from the last scheduled (but missed) ADCT-502 dose, permanently discontinue ADCT-502.
 
Third Occurrence:
 
Permanently discontinue ADCT-502.

3	
First Occurrence:
 
Hold ADCT-502 until improvement to <math>\leq</math> Grade 1 or Baseline. Up to 1 dose of ADCT-502 may be skipped to permit improvement, then continue ADCT-502 at 1 dose level below the original assigned dose in subsequent treatment cycles.
 
Second Occurrence:
 
Permanently discontinue ADCT-502.

4	Permanently discontinue ADCT-502.

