Thrombocytopenia (regardless of whether significant bleeding is present or not)	4	
Hold ADCT-502 until bleeding has stopped and improvement has occurred to <math>\leq</math> Grade 1. Up to 1 dose of ADCT-502 may be skipped to permit improvement.
 
First Occurrence:
 
Upon improvement to <math>\leq</math> Grade 1 within 21 days from last scheduled (but missed) ADCT-502 dose, continue ADCT-502 at 1 dose level below the original assigned dose in subsequent treatment cycles.
 
If improvement to CTCAE <math>\leq</math> Grade 1 does not occur within 21 days from the last scheduled (but missed) ADCT-502 dose, permanently discontinue

Adverse Event	Grade	ADCT-502 Management Guideline
		
ADCT-502.
 
Second Occurrence:
 
Upon improvement to <math>\leq</math> Grade 1 within 21 days from last scheduled (but missed) ADCT-502 dose, continue ADCT-502 at 2 dose levels below the original assigned dose in subsequent treatment cycles.
 
If improvement to <math>\leq</math> Grade 1 does not occur within 21 days from the last scheduled (but missed) ADCT-502 dose, permanently discontinue ADCT-502.
 
Third Occurrence:
 
Permanently discontinue ADCT-502.

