		
ADCT-502 dose, permanently discontinue ADCT-502.
 
Second Occurrence:
 
If improvement to <math>\leq</math> Grade 1 within 21 days from last scheduled (but missed) ADCT-502 dose, then continue ADCT-502 at 1 dose level below the original assigned dose in subsequent treatment cycles.
 
If improvement to <math>\leq</math> Grade 1 does not occur within 21 days from the last scheduled (but missed) ADCT-502 dose, permanently discontinue ADCT-502.
 
Third Occurrence:
 
Permanently discontinue ADCT-502.

Anemia	3	
Hold ADCT-502 until improvement to <math>\leq</math> Grade 1 or Baseline.
 
Up to 1 dose of ADCT-502 may be skipped to permit improvement.
 
Consider use of erythropoietin (EPO) as per institutional guidelines.
 
First Occurrence:
 
If improvement to <math>\leq</math> Grade 1 or Baseline prior to next scheduled dose, continue ADCT-502 at the original assigned dose at the next scheduled treatment cycle. If improvement to <math>\leq</math> Grade 1 or Baseline within 21 days from last scheduled (but missed) ADCT-502 dose, then continue ADCT-502 at 1 dose level below the original assigned dose in subsequent treatment cycles. If improvement to <math>\leq</math> Grade 1 or Baseline does not occur within 21 days from the last scheduled (but missed) ADCT-502 dose, permanently discontinue ADCT-502.
 
Second Occurrence:
 
If improvement to <math>\leq</math> Grade 1 or Baseline within 21 days from last scheduled (but missed) ADCT-502 dose, then continue ADCT-502 at 2 dose level below the original assigned dose in subsequent treatment cycles. If improvement to <math>\leq</math> Grade 1 or Baseline does not occur within 21 days from the last scheduled (but missed) ADCT-502 dose, permanently discontinue ADCT-502.
 
Third Occurrence:
 
Permanently discontinue ADCT-502.

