Anemia	4	
Hold ADCT-502 until improvement to <math>\leq</math> Grade 1 or Baseline.
 
Up to 1 dose of ADCT-502 may be skipped to permit improvement.
 
Consider use of EPO as per institutional guidelines.
 
First Occurrence:
 
If improvement to <math>\leq</math> Grade 1 or Baseline within 21 days from last scheduled (but missed) ADCT-502 dose, then continue ADCT-502 at 1 dose level below the original assigned dose in subsequent treatment cycles. If improvement to <math>\leq</math> Grade 1 or Baseline does not occur within 21 days from the last scheduled (but missed) ADCT-502 dose,

Adverse Event	Grade	ADCT-502 Management Guideline
		
permanently discontinue ADCT-502.
 
Second Occurrence:
 
If improvement to <math>\leq</math> Grade 1 or Baseline within 21 days from last scheduled (but missed) ADCT-502 dose, then continue ADCT-502 at 2 dose level below the original assigned dose in subsequent treatment cycles. If improvement to <math>\leq</math> Grade 1 or Baseline does not occur within 21 days from the last scheduled (but missed) ADCT-502 dose, permanently discontinue ADCT-502.
 
Third Occurrence:
 
Permanently discontinue ADCT-502.

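### Sections 5.1 to 5.3 set every resume dose from the original assigned dose with no cap at the current dose, so unless occurrences are pooled over all toxicities a patient already reduced for one can be directed upward after another

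*Protocol*

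**What the plan says.** Twelve rows in Protocol Sections 5.1 to 5.3 name a resume dose. Each gives the original assigned dose, or one or two levels below it.

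- **Return to the original dose, open-ended (3 rows).** For Grade 4 neutropenia, and for Grade 3 neutropenia or thrombocytopenia without bleeding, the first-occurrence instruction after recovery is "within 21 days from last scheduled (but missed) ADCT-502 dose, then continue ADCT-502 at original assigned dose in subsequent treatment cycles". The general Grade 2 row in Section 5.1 has "continue ADCT-502 at the original assigned dose level in subsequent treatment cycles".
- **Return to the original dose, next cycle only (4 rows).** For Grade 3 anemia that recovers before the next dose is due: "continue ADCT-502 at the original assigned dose at the next scheduled treatment cycle". Grade 3 AST/ALT and Grade 2 and Grade 3 hyperbilirubinemia have equivalent wording in Section 5.3.
- **Reductions.** A first Grade 4 thrombocytopenia leads to "continue ADCT-502 at 1 dose level below the original assigned dose in subsequent treatment cycles", and a second to "continue ADCT-502 at 2 dose levels below the original assigned dose in subsequent treatment cycles".

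The tables speak of first, second and third occurrences without saying whether these are counted per row, per event or over all toxicities. Section 5 does not say that a reduction is kept.

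Text elsewhere bears on the point:

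- The opening of Section 5 leaves resumption after a suspension to the investigator in consultation with the sponsor.
- Section 5.1 introduces its own table with "the following may serve as a guidance to investigators".
- Section 4.6 and the Part 1 synopsis bar dose escalation within a patient, but Section 4.6 also lets Part 1 patients be offered the recommended dose for expansion (RDE) once it is known.
- Section 4.6.1 has the Dose Escalation Steering Committee (DESC) oversee both parts.

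**The concern.** A resume rule anchored to the original dose is harmless while the patient is still on that dose. Once the patient has been reduced, the same words direct an increase. A second, different toxicity can therefore raise the dose, which is the opposite of what a toxicity table is for.

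The drug is a cytotoxic conjugate in a first-in-human study, and the rise would come just after a new Grade 2 to 4 event in a patient who has already needed a reduction. The stake is patient safety. The dose-escalation model and the MTD are untouched, because the DLT window is Cycle 1.

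**Working it through.** The plan gives no figure to reproduce, so the check codes the tables and enumerates what they direct.

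**Step 1. Code the rows.** Entries are levels relative to the original assigned dose; *stop* is permanent discontinuation.

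| Section | Row | First | Second | Third |
|---|---|---|---|---|
| 5.1 | Other event, Grade 2 | 0 | −1 | stop |
| 5.1 | Other event, Grade 3 | −1 | stop | |
| 5.2 | Febrile neutropenia, Grade 3 | −1 | stop | |
| 5.2 | Thrombocytopenia with bleeding or transfusion, Grade 3 | −1 | −2 | stop |
| 5.2 | Thrombocytopenia, Grade 4 | −1 | −2 | stop |
| 5.2 | Neutropenia, or thrombocytopenia without bleeding, Grade 3 | 0 | −1 | stop |
| 5.2 | Neutropenia, Grade 4 | 0 | −1 | stop |
| 5.2 | Anemia, Grade 3 | 0* or −1 | −2 | stop |
| 5.2 | Anemia, Grade 4 | −1 | −2 | stop |
| 5.3 | AST/ALT, Grade 3 | 0* or −1 | −2 | stop |
| 5.3 | Hyperbilirubinemia, Grade 2 | 0* or −1 | stop | |
| 5.3 | Hyperbilirubinemia, Grade 3 | 0* or −1 | stop | |

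*Only with recovery before the next dose; names only the next cycle. For Grade 2 hyperbilirubinemia the return is printed above the first-occurrence heading. It is coded as first occurrence because the second is discontinuation.

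Seven rows can return to 0. All twelve can give −1 at some occurrence. Five can give −2.

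**Step 2. Worked example.** Doses are from Table 9 (Section 18.4.1): 30, 60, 120, 150, 180, 210, 240, 300, 350, 400, 450, 500 µg/kg. The patient is assigned 240.

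- First Grade 4 thrombocytopenia: 210. Then first Grade 4 neutropenia: 240. 240/210 = 1.143, so +14%.
- Second Grade 4 thrombocytopenia: 180. Then first Grade 4 neutropenia: 240. 240/180 = 1.333, so +33%.
- From 180, a first Grade 3 febrile neutropenia instead: 210. 210/180 = 1.167, so +17%.

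**Step 3. Count pairs under row-by-row counting.** A pair is a reduction in one row followed by a first occurrence in a different row.

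- Ordered pairs: 12 × 11 = 132.
- After a one-level reduction, a rise is possible when the later row is a return row: 7 × 11 = 77.
- The later row is one of the three open-ended return rows: 3 × 11 = 33. The other 77 − 33 = 44 need early recovery and name only the next cycle.
- Pairs that take just two events: (5 × 7) + (4 × 6) = 59. The remaining 3 × 6 = 18 need a third event, because in three rows the reduction comes only at the second occurrence.
- After a two-level reduction: 5 × 11 = 55 pairs, and all 55 can direct a rise, since every first occurrence resumes at 0 or −1.

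**Step 4. Change the counting rule.** Counting by event name removes some pairs (for example Grade 4 then Grade 3 anemia) but leaves thrombocytopenia followed by neutropenia. With occurrences pooled over all toxicities, enumerating every sequence of up to three events gives 0 rises.

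**Step 5. Size of the rise, from Table 9.**

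| Assigned dose | One level down to original | Two levels down to original | Two levels down to one |
|---|---|---|---|
| 180 to 500 | +11% to +25% | +25% to +50% | +12.5% to +25% |
| 150 | 150/120 = +25% | 150/60 = +150% | 120/60 = +100% |
| 120 | 120/60 = +100% | 120/30 = +300% | 60/30 = +100% |
| 60 | 60/30 = +100% | none | none |

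No path goes above the original dose.

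**The case against.** The strongest reply is that the protocol, read as a whole, already prevents this. Section 4.6 bars within-patient escalation without any exception for resuming treatment. The one upward route it allows is the move to the RDE, which the Amendment 2 summary itself describes as intra-patient escalation. That suggests the sponsor uses the term for any rise in an enrolled patient's dose. Part 2, where no bar is stated, was never run (SAP Section 3.3). Six of the seven return rows begin with a hold, and the seventh is guidance that says to consider one, so a rise after a hold passes through sponsor consultation. Row-by-row counting is not written down, and the pair counts mix two-event and three-event paths.

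Much of this is fair. The counting rule is an ambiguity, not an explicit instruction; 59 is the count for two-event paths; and clinical judgement would often stop a rise.

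The reply still does not dispose of the point. The Section 4.6 bar sits in the cohort-escalation text, Section 5 does not refer to it, and a return to an assigned dose is not plainly escalation. If the bar does apply, it contradicts the tables. Pooled counting is stated nowhere and fits poorly with the febrile neutropenia row, whose second-occurrence rule speaks of that same event recurring. Sponsor consultation and DESC oversight set no dose limit. Early termination reduces the practical consequence but does not repair the rule.

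**Conclusion.** The concern holds. Unless occurrences are pooled over all toxicities, the tables can direct a dose above the current one after a new toxicity. For assigned doses of 180 µg/kg or more the rise is 11% to 50%; larger steps arise only at assigned doses of 60, 120 and 150 µg/kg.

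This rests on three assumptions: occurrences are counted per row or per event; dose levels are those of Table 9; and the Part 1 escalation bar does not silently override Section 5. Section 2.4 lists a ladder without 150 and 210; on that ladder one level below 240 is 180, and the one-level return becomes +33%.

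The pair counts show how widely the wording reaches. They say nothing about how often it would matter, and the documents give no frequency. The discontinuation, infusion-reaction and LVEF rows are not affected. This should be fixed, because the written rule points the wrong way on safety and the correction is nearly free.

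**What to change.** Add at the opening of Section 5, for both parts: *Dose reductions for toxicity are not reversed. The resumed dose is the lower of the current dose and the dose given in the table.* The rows then need no rewriting, and the counting rule no longer affects whether a dose can rise.

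As a secondary point, if the Section 4.6 move to the RDE is kept, add one sentence. It should say that the move does not raise the dose of a patient already reduced for toxicity to or below the RDE unless the sponsor agrees, and that otherwise the RDE becomes the reference dose for Section 5.

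The cost is an amendment of two sentences plus one, with no added visits, tests or patients. For patients already treated, the exposure and infusion listings planned in SAP Section 4.7.1 could be checked for any dose raised after a reduction.
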